During the feedback sessions, coaches will debrief about the encounters, answer questions, and discuss difficult patient interactions. The audio-recordings will be saved to a Box folder that only the clinician, study coordinator, coach and data manager have access to. These intervention audio-recordings will only be used to tailor the communication coaching sessions. Clinicians in the control arm will not get communication coaching.

Follow-up

Clinicians in both arms will then move into the follow-up phase. Clinicians will complete the follow-up survey. Then we will recruit and enroll 6 of the clinician's patients for follow-up measures (these will be different patients than those who participated in the baseline measures). We will follow the same procedure as those patients enrolled at baseline. Patients will be consented prior to the encounter and after consenting, they will be asked to complete a survey on a tablet in REDCap to obtain demographic and health information. We will seek the patient's permission to access their medical record to obtain information about their cardiology care and health status. Patients will audio-record the encounter on a tablet that saves the audio-recording directly to RedCap. The audio-recording is not stored locally on the device. After the visit, patients will also be asked questions to measure communication quality of their interaction and to complete the Interpersonal Processes of Care Survey. If a patient cannot complete this survey after the visit, we will call the participant to complete the survey over-the-phone, email the REDCap survey or mail a paper copy to the patient.

Measures: Patients who participate pre- and post-intervention will be asked questions about their demographics, health, healthcare utilization, and questions specific to their encounter with the enrolled clinician. The patients' responses to survey questions will not be shared with the clinician.

Enrolled clinicians will be asked questions about their demographics, clinical care history, and a survey about their confidence to communicate about behavior change, outcome expectations that communicating about behavior change positively impacts patient behavior, and barriers to communication. Clinicians will complete the survey about the communication aspects again at followup.

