For the pre-intervention and post-intervention phase, patients will be identified through the Maestro Care Report to identify enrolled clinician's patients who may be eligible. This report will be run by study personnel after the clinician has enrolled. We will oversample Black/African American patients and exclude patients at the eligibility screener to ensure that we achieve a sample of approximately 50% Black/African American. In order to avoid analytic issues related to correlated responses, we will select unique patients (i.e., if a patient has an encounter recorded at pre-intervention, he/she will be excluded from contributing an encounter at post-intervention). Thus, we will determine effects pre and post training of the clinician, not of individual patients.

Clinicians randomized to the intervention will identify up to an additional 6 eligible patients whose encounters will be recorded and used to guide the coaching session. These patients will not complete surveys and we will not record any information about them, other than the audio-recording. The clinician will be instructed to identify patients who meet the inclusion criteria and will obtain verbal consent, as outlined below.

Subject Recruitment, Consent and Compensation

Clinicians: We will work with the Division Chief of Cardiology to identify eligible clinicians.

The Division Chief of Cardiology will present the study at the Cardiology Grand Rounds and connect study investigators with the Clinic Leaders for each participating clinic. Study investigators will meet with clinic leaders to discuss best methods for recruiting (e.g., going to a staff meeting, email, etc.). The study will also be publicized on the Division internal website and the study team may make presentations at division conferences, with approval and support of the Division. Recruitment materials will be uploaded to the IRB once they are finalized. No recruitment will occur until these materials have been approved by the IRB.

For in-person clinician recruitment, study staff will meet with the clinician and obtain written consent or econsent via REDCap and ask the clinician to complete the baseline survey. To minimize the burden of the consent process on clinicians and to accommodate their schedules, clinicians may enroll with study staff in small groups, at faculty meetings, or individually. Clinicians will be offered the opportunity to ask questions in private and/or conduct consent in private.

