Clinicians randomized to the intervention will identify and obtain verbal consent from up to an additional 6 patients to provide audio-recordings for the intervention feedback sessions. The study coordinator will provide the consent script to clinicians and ask that they follow it. Using this script, clinicians will introduce the study to eligible patients. The clinician will ask patients if they will allow for their visit to be audio-recorded as part of a study to understand the way the provider communicates. The clinician will obtain verbal consent from the patient. The clinician will make it clear that the audio recording is to observe the clinician and not the patient. The clinician also will let the patient know that if they refuse, it will not affect the care they receive. Only when the patient gives consent will the clinician turn on the audio-recorder. We request a waiver of written consent because it would not be

possible for clinicians to ask patients to sign a written consent form as it would interrupt clinic flow and make the study infeasible. We anticipate that up to 150 patients will verbally consent to allow for their visit to be audio-recorded. These patients will not be compensated for their participation. Patients who complete the pilot will not be compensated.

Risk/Benefit Assessment

The study involves minimal risk. The only risk to participation in this study is the potential breach of confidentiality during audio recordings and assessment. Some of the questions participants will be asked might make them feel uncomfortable. All participants may refuse to answer any of the questions and may stop their participation in this study at any time. Due to the sensitive nature of the survey questions, study staff will take every precaution to secure the privacy of participant information. As this is an NIH-funded study a Certificate of Confidentiality (COC) from the NIH has been issued to further protect the data. Potential benefits are that the clinicians might learn more effective ways to communicate with their patients. Information learned from this study may also benefit clinicians and patients in the future.

Costs to the Subject:

There are no costs to the participant as a result of participating in the study.

Data Analysis & Statistical Considerations:

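### The unique-patient rule bars only baseline patients from the post-period, so patients recorded for coaching could re-enter as outcome patients, in the intervention arm only

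*Protocol*

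**What the plan says.** The protocol gives the reason for the rule and then its scope, both under Selection of Subjects. The reason is: "In order to avoid analytic issues related to correlated responses, we will select unique patients". The scope follows directly, as an explanation of what unique means: "if a patient has an encounter recorded at pre-intervention, he/she will be excluded from contributing an encounter at post-intervention". The Follow-up section has the same scope; of the six post-period patients per clinician it says that "these will be different patients than those who participated in the baseline measures".

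A further group of patients is recorded between the two periods. Selection of Subjects says: "Clinicians randomized to the intervention will identify up to an additional 6 eligible patients whose encounters will be recorded and used to guide the coaching". On the data kept, it says: "These patients will not complete surveys and we will not record any information about them, other than the audio-recording". Such patients exist in one arm only, because "Clinicians in the control arm will not get communication coaching" (Randomization and Intervention).

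The eligibility criteria are common to both types of patient participant and admit return as well as new patients. Post-period candidates come from a Maestro Care report run for each clinician, followed by an eligibility screener whose items are not listed. The SAP's analysis and power sections do not take up the point. The opening part of the SAP was not available to me, so I make no claim about it.

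**The concern.** A patient recorded for coaching remains, on the text, an eligible return patient of an intervention clinician when post-period recruitment opens. Nothing in the stated rule removes that patient, and the study has no list to match against the report.

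The post-period encounter is meant to show whether a coached clinician communicates better with patients in general. A re-entering patient is a different case. The coach has already listened to that patient's visit and discussed it with the clinician. The clinician chose that patient, whereas other outcome patients come from a report. The patient has also been through a recording request from the clinician, in which "The clinician will make it clear that the audio recording is to observe the clinician and not the patient".

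Control clinicians have no such patients, so randomization cannot balance the exposure. Because no identifier is kept, re-entry could not be found or adjusted for afterwards from study data. The outcomes affected are the communication count (Hypotheses 1a and 2a) and the patient-rated IPC score (1b and 2b).

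**Working it through.** **1. The plan's own counts.** Selection of Subjects gives up to 50 clinicians, 500 survey patients, 150 coaching patients and 20 pilot patients.
- Coaching patients: 25 intervention clinicians (half of 50, assuming equal allocation) × 6 = 150, as stated.
- Total: 50 + 500 + 150 + 20 = 720, as stated. The total counts coaching patients as separate people.
- Post-period sample in the power section: 40 clinicians × 6 = 240, so 20 × 6 = 120 per arm.

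**2. The plan's detectable effect for Hypothesis 1a.** I used the cluster-randomized formula for two rates, c = 1 + (z₀.₉₇₅ + z₀.₈₀)² × [(r₀ + r₁)/m + CV²(r₀² + r₁²)] / (r₁ − r₀)². The inputs are c = 20 clinicians per arm, m = 6 and r₀ = 1.0. Solving for r₁ gives 1.47, 1.60 and 1.79 at CV 0.2, 0.35 and 0.5. The SAP table has 1.5, 1.6 and 1.8, so the yardstick is sound.

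**3. Expected overlap.** Assume that each intervention clinician has N eligible patients, that the maximum of 6 were recorded for coaching, and that the 6 outcome patients are a simple random draw from the N. Expected overlap is 6 × 6/N per clinician and 20 × 36/N over the arm. The documents do not give N. A clinician with a half-day clinic per week qualifies, so small panels are possible.

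**4. Effect on the intervention mean.** Let s = 6/N be the share of re-entrants. Assume, for illustration only, that their statement rate is 1.5 times that of other patients. The mean is then multiplied by 1 + 0.5s.

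| Assumed N | Expected overlap of 120 | Share s | Control arm | Mean multiplied by |
|---|---|---|---|---|
| 50 | 14.4 | 12% | 0 | 1.06 |
| 100 | 7.2 | 6% | 0 | 1.03 |
| 200 | 3.6 | 3% | 0 | 1.015 |
| 300 | 2.4 | 2% | 0 | 1.01 |

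Overlap is proportional to the number recorded: with 3 coaching patients per clinician instead of 6, each overlap figure halves.

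**5. Effect on type I error for Hypothesis 1a.** Under no true effect and CV 0.2, the standard error of the log rate ratio is √[(2/6 + 2 × 0.2²)/20] = √(0.4133/20) = 0.144. Shifts of ln 1.06, ln 1.03 and ln 1.015 turn a two-sided 5% test into about 6.9%, 5.5% and 5.1%. A larger CV gives a larger standard error and a smaller change.

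**The case against.** The strongest reply is that the documents already treat the groups as different people. The protocol names two types of patient participant, calls the coaching patients additional, and adds them separately into the 720. That stands as evidence of intent. It is a classification and a headcount, however, not an exclusion criterion. The screener might ask about earlier recordings, since its items are not listed, but the protocol's own statement of the rule stops at baseline patients.

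Four further points stand and limit the concern.
- A reader might infer that the rule fails at its job. It does not. Its stated aim is to avoid correlated responses, and coaching recordings are never outcome data, so a re-entering coaching patient still contributes one outcome.
- A reader might infer that coaching patients cannot be identified at all. The clinician knows who was recorded, study staff can access the audio, and the patient can be asked. What is missing is a recorded identifier to match against the report.
- A reader might infer that the results are inflated. All outcome patients, in both arms, are invited to a study of clinician communication and record their own visit. Much of the awareness of observation is therefore common to the arms; only the prior exposure differs. The documents do not fix the direction of its effect.
- A reader might assume that post-period visits follow soon after coaching. No interval is given, and a patient just seen may be less likely than others to return within the recruitment window. Patients who already agreed to one recording may, on the other hand, agree more readily to a second.

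**Conclusion.** The gap is real but minor. On the text, coaching patients are not barred from the post-period, they exist in one arm only, and no recorded identifier allows their removal. The plausible overlap is about 2 to 14 of 120 intervention-arm patients for assumed panels of 300 down to 50. It is fewer if clinicians record under 6 patients or return intervals are long.

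Even with an assumed 1.5-fold rate in re-entrants, the intervention mean moves by about 1% to 6%, against a detectable rate ratio of 1.5 to 1.8. The panel sizes, the random draw and the 1.5-fold rate are all assumptions. The documents do not support a claim that the primary result would be materially biased, or biased upward. They do support the narrower claim that an avoidable exposure, confined to one arm and invisible afterwards, has been left open.

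**What to change.** In Selection of Subjects and in Follow-up, extend the rule so that a patient with any earlier visit recorded for this study, whether at baseline, for coaching or in the pilot, is ineligible for the post-period. Apply it with one yes/no item on the post-period eligibility screener, worded and asked identically in both arms: has an earlier visit of yours been audio-recorded for this study? A yes means that the next eligible patient is approached instead.

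The cost is one sentence in each section and one screener item. No identifiers need be collected from coaching patients. The 240 post-period patients, the models and the power stay as they are.

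There are two small downsides. A yes from someone who was not a baseline or pilot patient may hint to the recruiter that the clinician is in the intervention arm. A few clinician-selected patients are also removed from that arm only. Both seem acceptable for a rule that carries out what the sponsor's headcount already implies.

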We propose a two-arm cluster randomized controlled design, in which the unit of randomization is the clinician. Up to fifty cardiology clinicians will be randomly assigned to either the coaching intervention or to a control condition. We will recruit up to 50 clinicians to ensure that we have at least 40 clinicians with complete pre- and post-intervention measures. Although the unit of randomization is the clinician, the unit of evaluation is the patient: 10 patients per clinician (4 pre-intervention and 6 post-intervention) who get cardiology care from the enrolled clinicians will consent to audio-recording of their encounters and to completing the surveys. The intervention will be delivered in the clinic or via video-conference (Skype or Facetime), providing individual coaching and professional feedback on the communication behaviors encounters. We will also measure Press Ganey scores by clinician pre- and post-intervention. We will ask that learners (i.e. medical students, fellows, interns, etc.) not be in the room during recorded encounters with enrolled patient participants.

Pre-Intervention

We will work with the Duke Division Chief of Cardiology to recruit clinicians across Duke's ambulatory cardiology clinics. Enrolled clinicians will complete a baseline and demographics survey. Then, for each enrolled clinician, we will recruit and enroll 4 of their patients for baseline measures. Patients will be consented prior to the encounter. After consenting, they will be asked to complete a survey on a tablet in an application that uses REDCap to obtain demographic and health information. We will seek the patient's permission to access their medical record to obtain information about their cardiology care and health status. Patients will audio-record the encounter on a tablet that saves the audio-recording directly to REDCap. The audio-recording is not stored locally on the device. After the visit, patients will complete a survey on the tablet in REDCap with questions to measure communication quality of their interaction with the clinician and will complete the Interpersonal Processes of Care Survey. If a patient cannot complete this survey after the visit, we will call the participant to complete the survey over-the-phone, email the REDCap survey, or mail a paper copy to the patient. After patients complete the survey, their participation in the study is complete.

Randomization and Intervention

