After 4 patients have been enrolled and successfully completed the baseline measures, the clinician will be randomized to either the intervention arm or the control arm. The intervention will contain elements of Motivational Interviewing coaching but also will teach providers how to address patient emotion and increase the efficiency of their visits. Clinicians randomized to the intervention will receive a tailored communication coaching intervention that includes didactic elements, audio recording encounters and providing feedback, and role-playing. They will receive a 'pocket card' that they can use to remind themselves about what they've learned in the coaching sessions.

The clinicians will meet in-person or via video conference three times with the coach.

Session #1: The first meeting with providers will give an overview of the study and communication techniques.

Then, clinicians will audio-record up to 3 clinical encounters with patients. These audio-recordings are the only data from the patients as patients do not complete surveys and we do not obtain any

information from their medical records. The consent process is outlined in the consent section below. The clinician uploads the audio-recording immediately to a shared Box folder and deletes the recording from the encrypted device, an iPod Touch.

The coach listens to the recordings then schedules a coaching session with the clinician. Session #2: The coach meets with the clinician to provide tailored feedback based on the audiorecordings. At the end of the session, the clinician will set a goal for a communication skill they will try to use in future encounters.

Clinicians then repeat this process by recording up to 3 new clinical encounters following the same procedures.

The coach listens to the audio-recordings and schedules another coaching session.

Session #3: The coach meets with the clinician to provide tailored feedback based on the audiorecordings. At the end of the session, the clinician will set a goal for a communication skill they will try to use in future encounters.

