For recruitment via email, Clinic leaders will send out an email introducing the PI and study coordinator. The PI will follow up with the clinicians and the study coordinator will send a link where clinicians can express interest or to opt out of the study. Due to the possibility that clinicians may miss recruitment emails, the PI and CRC will contact the clinicians more than once in order to determine if the clinician would like to enroll or opt-out.

Patients: With a HIPAA Waiver of Authorization, we will run a report in Maestro Care report to identify eligible patients by clinician at pre-intervention and at post-intervention. At their visit, clinic staff (patient service associates, nurses, etc) will ask the patient if he/she is interested in a study looking at clinician communication. Interested patients will be referred to the study recruiter for screening and, if eligible, to conduct the informed consent process in a private location in the clinic. Patients who agree to participate will be consented at that time using the REDCap econsent. In addition, since family members and friends are often very active in patient's health care decisions, they will be approached for consent to allow us to code this comments during the clinic visit. If a legal guardian is present, study staff will obtain assent from minors accompanying an eligible patient. The study team member will be present during the consent process to answer questions. Patients will receive a copy of the consent form via email or a copy will be mailed to them. Patients who do not wish to participate will be recorded in the study's REDCap database as refusing participation. Up to 500 patients (10 per clinician) will be enrolled in order to produce audio-recordings of encounters, before and after intervention. These patients will receive \$20 for completing the study (audio-recording and post-encounter survey).

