## Analysis Plan

### F.2 Aim 1 analyses:

*Hypothesis 1a:* As compared to the control group, clinicians randomized to the intervention will have a **greater mean number objective measures of communication quality** in encounters with both Black and White patients combined and in each race subgroup.

The goal of the primary Hypothesis (1a) is to determine the efficacy of the clinician communication coaching intervention versus usual care on an objective measure of the quality of communication from baseline to post-training. Additionally, we are interested the intervention effect within Black patients and White patients separately. The quality of communication will be assessed at both baseline encounters and post-training encounters by a summary of clinician encounter counts derived from the audio recordings. We plan to use mixed-effects models as our primary analytic strategy because they will appropriately account for the intracluster correlation of multiple patient encounters for each clinician. The mixed-effects model for Hypothesis 1a will have the following form:

$\log(\mu_{ik}) = \mu_0 + \mu_1(int) + \mu_2(premean_k) + \mu_3(clinsex_k) + \mu_4(clintype_k) + b_{0k}$ , where  $Y_{ik}$  is the number of quality communication statements for patient  $i$  in the post-period clustered within physician  $k$ , and  $Y_{ik}$  is assumed to be Poisson with mean and variance equal to  $\mu_{ik}$ . The fixed effects in the model include indicator variables intervention group (*int*), each clinician's mean number of quality communication statements per conversation prior to the intervention, and the clinician stratification variables. The random intercept,  $b_{0k}$ , is normally distributed and accounts for dependence of encounters within clinicians. PROC GLIMMIX (with the quadrature option) in SAS (SAS Inc., Cary, NC) will be used to fit the mixed-effects Poisson model and test the primary hypothesis (1a). Specifically, if  $\mu_1$  is positive and significantly different than zero, this provides evidence of greater communication quality among patients and clinicians in the intervention group as compared to the control group.

The analysis for Hypothesis 1a will also be conducted for encounters with white and black patients separately.

*Hypothesis 1b:* Black patients and White patients seen by clinicians in the intervention group will report **higher mean quality of patient-centered care** compared to patients seen by control group clinicians.

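### Post-period patients are recruited after clinicians are randomised to open arms, with no stated masking or order of approach, and the 1a and 1b models adjust for no patient characteristic

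*Protocol*

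**What the plan says.** **Sequence.** Protocol, Randomization and Intervention: "After 4 patients have been enrolled and successfully completed the baseline measures, the clinician will be randomized". Protocol, Follow-up: "Then we will recruit and enroll 6 of the clinician's patients for follow-up measures", and "these will be different patients than those who participated in the baseline measures".

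**Open arms.** The same part of the protocol says: "Clinicians in the control arm will not get communication coaching". No sham contact is described, so clinicians know their arm.

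**Entry of patients.** Protocol, Subject Recruitment, Consent and Compensation: "clinic staff (patient service associates, nurses, etc) will ask the patient if he/she is interested in a study looking at clinician communication". After that, "Interested patients will be referred to the study recruiter for screening". Study personnel list possible patients from a Maestro Care report (Protocol, Selection of Subjects), but no consecutive or random order is set for working through it.

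**Models.** SAP F.2, Hypothesis 1a: "The fixed effects in the model include indicator variables intervention group", followed by the clinician's pre-period mean count (premean), clinician sex and clinician type, with a clinician random intercept. Hypothesis 1b has arm, clinician sex and clinician type, and sets baseline patient data aside. The protocol's own 1a model also has no patient term. Patient race enters only the Aim 2 models and the separate runs by race.

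**Available data.** Patients complete a survey before the encounter "to obtain demographic and health information" (Protocol, Pre-Intervention; Follow-up repeats the procedure).

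**The concern.** Randomising clinicians balances clinicians, and the patients they would see whatever the arm. It does not balance patients who are approached and agree once the arm has been assigned. If the people who enter differ between arms, the arm coefficient in 1a or 1b contains that difference along with any coaching effect. Hypothesis 1b is the more exposed: its outcome is the patient's own rating, and its model has no baseline term. The plan already collects patient information before the visit that could reduce part of this risk, but it does not use that information in either model.

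**Working it through.** **1. Reproduce the plan's figure.** Inputs from the SAP, Power and Sample Size Considerations and its table: 20 clinicians per arm, m = 6 post-period patients each, baseline rate r0 = 1.0, CV 0.2 / 0.35 / 0.5, 80% power, type I error 5%. The protocol specifies two-sided tests. The formula for two Poisson rates in a cluster-randomised design is

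c = 1 + (1.96 + 0.84)² × [(r0 + r1)/m + CV²(r0² + r1²)] / (r1 − r0)².

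Setting c = 20 and solving for r1 gives 1.47 / 1.60 / 1.79, which round to the stated 1.5 / 1.6 / 1.8. The power figures are sound and are not in question here.

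**2. Implied standard error of log IRR.** SE = ln(detectable IRR)/2.80. At CV 0.2, ln(1.47)/2.80 = 0.138. At CV 0.5, ln(1.79)/2.80 = 0.208.

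**3. Error rate for 1a under an assumed recruitment shift.** With no true effect and mean counts shifted by a fraction b between arms, the error rate is P(|Z + ln(1 + b)/SE| > 1.96).

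| Assumed b | ln(1 + b) | Error rate, SE 0.208 to 0.138 |
|---|---|---|
| 5% | 0.049 | about 6% |
| 10% | 0.095 | 7-11% |
| 20% | 0.182 | 14-26% |

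**4. What such a shift requires.** For a binary patient factor with rate ratio RR and prevalence p0 (control) and p1 (intervention), the spurious IRR is [1 + p1(RR − 1)]/[1 + p0(RR − 1)]. Take p0 = 50%.
- RR 1.5, p1 = 60%: 1.30/1.25 = 1.04.
- RR 1.5, p1 = 70%: 1.35/1.25 = 1.08.
- RR 2.0, p1 = 70%: 1.70/1.50 = 1.13.
- A 20% shift needs p1 = 80% at RR 2.0 (1.80/1.50), or p1 = 100% at RR 1.5 (1.50/1.25). This is why the last row above is extreme.

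**5. Does premean protect 1a?** A simulation (2,000 runs per scenario, Poisson regression, no true effect, CV 0.35) set prevalence at 50% in both arms before randomisation and shifted it to 70% in the intervention arm afterwards.

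| Factor RR | Unadjusted IRR | With premean | With premean and the patient factor |
|---|---|---|---|
| 1.5 | 1.08 | 1.08 | 1.00 |
| 2.0 | 1.14 | 1.14 | 1.00 |

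Premean leaves a shift that arises after randomisation untouched. The last column adjusts for the simulated factor itself, so it shows the best that adjustment can do.

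**6. Hypothesis 1b.** In SD units, SE = √[2(1 + 5·ICC)/120], which is 0.132 at ICC 0.01 and 0.158 at ICC 0.1. An assumed shift of 0.1 SD gives an error rate of 10-12%; 0.2 SD gives 24-33%.

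**The case against.** The plan has more protection than the model equations suggest.
- Candidates come from a report run by study personnel, not from the clinician.
- The invitation is described once for both arms, and follow-up recruitment repeats the procedure used before randomisation.
- Refusals are recorded.
- Variables are to be described overall and within clinician.
- Premean absorbs stable clinician or clinic differences in 1a.
- Race is partly controlled: about 50% Black patients are sought, the SAP table assumes three patients per clinician in each race group, the analyses are repeated by race, and Aim 2 models it.

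All of this stands, and it narrows the point to a shift in patient mix that arises after randomisation. It does not close it. The report defines who may be eligible, not who is approached. The race target is not stated by arm or clinician and does nothing for other factors. Patients never approached would not appear among the refusals, and no comparison by arm is planned.

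A reader might infer that clinic staff and recruiters know the arm. The documents show this only for the clinician; for the others, all that can be said is that no masking is stated. A reader might also infer that easier or more engaged patients would inflate the intervention arm. Nothing in the documents fixes a direction, and the primary outcome is a count from recordings, not a patient rating. Nor do race, age, sex and visit type measure engagement, so adjustment answers only part of the concern.

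**Conclusion.** The point holds as a conditional risk. Enrolment after randomisation, open arms, first approach by clinic staff, and the absence of patient terms from 1a and 1b are all confirmed in the text. The part of the SAP before its Analysis Plan heading was not available, so statements of absence are limited to the text that was.

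A reader might go further and conclude that the primary estimate is biased. The documents do not support that: they neither show nor size a difference in recruitment between arms, and every shift in the working is an assumption. At the milder assumed imbalances the 1a distortion is modest. A spurious IRR of 1.04 to 1.13 is about 10% to 31% of ln(1.5) on the log scale, against a smallest detectable IRR of 1.5. The error rates use a normal approximation and the plan's own power inputs, without allowing for any precision gained from premean. The finding is a missed low-cost improvement, not an error in the plan.

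**What to change.** 1. In the 1a and 1b models, prespecify patient race, age, sex and new/return status as fixed effects, omitting race in the race-subgroup runs. All four are known before the visit. The documents do not list the survey items, so confirm that each is recorded.
2. Tabulate approached, refused and enrolled patients by arm, with their characteristics as far as the report, screener and survey hold them.
3. Where workable with existing staff, approach patients from the Maestro Care report in random order within race group. A strictly consecutive order would conflict with the oversampling of Black patients.
4. State whether clinic staff and recruiters are masked to arm. Requiring masking is a separate matter, as it may need an additional person.

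The cost is four more model terms, one table and a slightly less flexible clinic workflow. Items 1 and 2 can still be added before analysis if recruitment is complete. The covariates remove only measured differences and do not capture patient engagement, so item 3 is worth having as well.
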